### **3.3 SELECTION OF TRIAL POPULATION**

It is planned that 32 healthy male subjects will enter the study. Subjects will be recruited from the volunteers' pool of the trial site. Only male subjects will be included in the trial because no data on reproductive and developmental toxicology are available at this time.

A log of all subjects enrolled into the trial (i.e. who have signed informed consent) will be maintained in the ISF irrespective of whether they have been treated with investigational drug or not.

#### **3.3.1 Main diagnosis for trial entry**

The study will be performed in healthy subjects.

#### **3.3.2 Inclusion criteria**

Subjects will only be included in the trial if they meet the following criteria:

1. Healthy male subjects according to the assessment of the investigator, as based on a complete medical history including a physical examination, vital signs (blood pressure[BP], PR) including body temperature, 12-lead ECG, and clinical laboratory tests at screening visit
2. Japanese ethnicity, according to the following criteria:
  - born in Japan, have lived outside of Japan <10 years,
  - have parents and grandparents who are Japanese
3. Age of 20 to 45 years (inclusive) at screening visit
4. Body mass index (BMI) of 18.5 to 25.0kg/m^2 (inclusive) at screening visit
5. Signed and dated written informed consent prior to admission to the study, in accordance with Good Clinical Practice (GCP) and local legislation
6. Subjects who agree to minimize the risk of making their partner pregnant by fulfilling any of the following criteria starting from the first administration of trial medication until 90 days after last administration of trial medication
  - Use of adequate contraception by any of the following methods plus condom: intrauterine device, combined oral contraceptives that started at least 2 months prior to the first drug administration.
  - Vasectomized (vasectomy at least 1 year prior to enrolment)
  - Surgical sterilization (including bilateral tubal occlusion, hysterectomy or bilateral oophorectomy) of the subject's female partner

#### **3.3.3 Exclusion criteria**

Subjects will not be allowed to participate, if any of the following general criteria apply:

Proprietary confidential information © 2021 Boehringer Ingelheim International GmbH or one or more of its affiliated companies

1. Any finding in the medical examination (including BP, PR or ECG) deviating from normal and assessed as clinically relevant by the investigator at screening visit
2. Repeated measurement of systolic blood pressure outside the range of 100 to 140 mmHg, diastolic blood pressure outside the range of 50 to 90 mmHg, or pulse rate outside the range of 50 to 90 bpm at screening visit
3. Any laboratory value outside the reference range that the investigator considers to be of clinical relevance at screening visit
4. Any evidence of a concomitant disease assessed as clinically relevant by the investigator
  - Gastrointestinal, hepatic, renal, respiratory, cardiovascular, metabolic, immunological or hormonal disorders
  - Diseases of the central nervous system (including but not limited to any kind of seizures or stroke), and other relevant neurological or psychiatric disorders
  - Chronic or relevant acute infections including viral hepatitis, human immunodeficiency virus (HIV) and/or syphilis.
5. History of cholecystectomy or other surgery of the gastrointestinal tract that could interfere with the pharmacokinetics of the trial medication (except appendectomy or simple hernia repair)
6. History of relevant orthostatic hypotension, fainting spells, or blackouts
7. History of relevant allergy or hypersensitivity (including allergy to the trial medication or its excipients)
8. Use of drugs within 30 days of planned administration of trial medication that might reasonably influence the results of the trial (including drugs that cause QT/QTc interval prolongation)
9. Intake of an investigational drug in another clinical trial within 60 days of planned administration of investigational drug in the current trial, or concurrent participation in another clinical trial in which investigational drug is administered
10. Smoker (more than 10 cigarettes or 3 cigars or 3 pipes per day)
11. Inability to refrain from smoking on specified trial days
12. Alcohol abuse (consumption of more 24 g per day)
13. Drug abuse or positive drug screening
14. Blood donation of more than 400 mL within 12 weeks or 200 mL within 30 days or plasma donation within 2 weeks prior to trial drug administration, or intended blood donation during the trial
15. Intention to perform excessive physical activities within one week prior to the administration of trial medication or during the trial
16. Inability to comply with the dietary regimen of the trial site
17. A marked baseline prolongation of QT/QTc interval (such as QTc intervals that are repeatedly greater than 450 ms) or any other relevant ECG finding at screening visit
18. A history of additional risk factors for *Torsade de Pointes* (such as heart failure, hypokalaemia, or family history of Long QT Syndrome)

Proprietary confidential information © 2021 Boehringer Ingelheim International GmbH or one or more of its affiliated companies

19. Subject is assessed as unsuitable for inclusion by the investigator, for instance, because the subject is not considered able to understand and comply with study requirements, or has a condition that would not allow safe participation in the study
20. ALT (alanine transaminase), AST, or serum creatinine exceed upper limit of normal range at screening visit, confirmed by a repeat test
21. Orthostatic hypotension during orthostatic testing at between Day -3 to -1, that the investigator considers to be of clinical relevance.
22. A positive for SARS-CoV-2 specific test and clinical symptoms suggestive for this disease at screening visit or within 3 days prior to admission to trial site.

For study restrictions, refer to Section [4.2.2](#).

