## Safety measures

The following safety measures will be applied in order to minimize the risk for healthy volunteers:

- Careful dose selection, no dose will be included which has not been previously studied in the FIH study.
- The dose escalation factor is limited to 2.
- Repeated safety laboratory tests will be performed before and during the treatment period (refer to [Flow Chart](#) and see Section [5.2.4](#)). This will also include sensitive serum markers to detect early skeletal muscle injury.
- An ECG monitoring up to Day 5 (96 h post dose) will be performed to cover the anticipated period of highest drug exposure. Continuous ECG measurement will be performed over 4 hours post dose. Dose escalation will be stopped immediately, if at least 2 subjects at one dose level show relevant QT prolongation (see Section [3.3.4.2](#) for details).
- Orthostatic testing will be performed prior to and following study drug administration at the time points indicated in the Flow Chart to assess hemodynamic effects of BI 474121. Dose escalation will be stopped, if clinical symptoms are observed in more than 1 subject (severe) or in more than 3 subjects (moderate) in one dose group.

Proprietary confidential information © 2021 Boehringer Ingelheim International GmbH or one or more of its affiliated companies

- Only if the respective dose of BI 474121 is safe, shows acceptable tolerability, and if no stopping criterion was met (see Section [3.3.4.2](#)), the next higher dose will be given not earlier than 7 days after first dosing of the previous dose group (referring to the 1st subject of each respective dose group). A documented Safety Review must take place prior to each dose escalation (see Section [3.1](#)).
- The subjects will stay at the trial site for at least 48 hours after study drug administration. Based on observed half-life of BI 474121 of ~20 hours in FIH study, this is expected to cover the period of highest risk / peak effect.
- During in-house confinement, the subjects will be under medical observation and thoroughly monitored for both expected and unexpected adverse events.
- SARS-CoV-2 specific test will be conducted at screening visit and within 3 days prior to admission to trial site. Subjects positive in the SARS-CoV-2 test are not eligible to the trial in accordance to exclusion criterion 25 and will be excluded from the trial.

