### 3.3.4 Withdrawal of subjects from treatment or assessments

Subjects may discontinue trial participation by withdrawing consent to trial participation as a whole ('withdrawal of consent') or by being removed from the trial by the investigator; please see Section 3.3.4.1 below.

If a subject discontinues trial participation prior to the administration of trial medication, the data of this subject will not be entered in the case report form (CRF) and will not be reported in the clinical trial report (CTR). If a subject discontinues trial participation after administration of trial medication, this will be documented and the reason for discontinuation of trial participation must be recorded in the CRF; in addition, the data will be included in the CRF and will be reported in the CTR.

At the time of discontinuation of trial participation, a complete end of trial examination will be performed, if possible, and the information will be recorded in the CRF. If the discontinuation occurs before the end of the REP (see Section [1.2.7](#)), the discontinued subject should if possible be questioned for AEs and concomitant therapies at or after the end of the REP in order to ensure collection of AEs and concomitant therapies throughout the REP, if not contrary to any consent withdrawal of the subject.

Since the risks of drug exposure of a pregnant partner of a study participant via the seminal fluid are yet unknown, adequate contraception as outlined in Section [3.3.2](#), is a prerequisite for participation in the study and is still necessary even if the subject withdraws consent or is removed from the trial.

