#### 3.3.4.1 Discontinuation of trial participation

An individual subject will discontinue trial participation if:

1. The subject wants to discontinue trial participation (withdrawal of consent), without the need to justify the decision
2. The subject has repeatedly shown to be non-compliant with important trial procedures and, in the opinion of both, the investigator and sponsor representative, is not willing or able to adhere to the trial requirements in the future
3. The subject needs to take concomitant medication that interferes with the investigational medicinal product or other trial treatment

Proprietary confidential information © 2021 Boehringer Ingelheim International GmbH or one or more of its affiliated companies

4. The subject can no longer participate in this trial for medical reasons (such as surgery, adverse events [AEs], or diseases)
5. An AE or clinically significant laboratory change or abnormality occurs that the investigator assesses as warranting discontinuation of trial participation. This may include cases of sustained symptomatic hypotension (BP <90/50 mmHg) or hypertension (BP >180/100 mmHg), clinically relevant changes in ECG requiring intervention, or unexplained hepatic enzyme elevations at any time during the trial
6. The subject has an elevation of AST and/or ALT  $\geq$ 3-fold upper limit of normal (ULN) and an elevation of total bilirubin  $\geq$ 2-fold ULN (measured in the same blood sample) and/or needs to be followed up according to the DILI checklist provided in the ISF
7. The patient experiences an infection with SARS-CoV-2 (see Section [5.2.4](#))

In addition to these criteria, the investigator may discontinue subjects at any time based on his or her clinical judgment.

Even if the trial participation is discontinued, the subject, given his agreement, will undergo the procedures for early trial treatment discontinuation and follow up as outlined in the [Flow Chart](#) and section [6.2.3](#).

In case of discontinuation of trial participation according to item #1 above, the investigator should be involved in the discussion with the subject and explain the options for continued follow up.

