- Prior to allocation of a subject to a treatment into a clinical trial, there must be documented evidence in the source data (e.g. medical records) that the trial participant meets all inclusion criteria and does not meet any exclusion criteria. The absence of records (either medical records, verbal documented feedback of the subject or testing conducted specific for a protocol) to support inclusion/exclusion criteria does not make the subject eligible for the clinical trial.

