|                              | 
stroke), and other relevant neurological or psychiatric disorders
 
8. History of relevant orthostatic hypotension, fainting spells, or blackouts
 
9. Chronic or relevant acute infections including viral hepatitis, human immunodeficiency virus (HIV) and/or syphilis.
 
(...)
 
To:
 
(...)
 
4. Any evidence of a concomitant disease assessed as clinically relevant by the investigator
 

- Gastrointestinal, hepatic, renal, respiratory, cardiovascular, metabolic, immunological or hormonal disorders

- Diseases of the central nervous system (including but not limited to any kind of seizures or stroke), and other relevant neurological or psychiatric disorders

- Chronic or relevant acute infections including viral hepatitis, human immunodeficiency virus (HIV) and/or syphilis.

 
5. History of cholecystectomy or other surgery of the gastrointestinal tract that could interfere with the pharmacokinetics of the trial medication (except appendectomy or simple hernia repair)
 
6. History of relevant orthostatic hypotension, fainting spells, or blackouts
 
(...)
 |
| Rationale for change  | To clarify the exclusion criteria for concomitant disease and medical history  |
| Section to be changed | Section 3.3.4.2  |
| Description of change | 
From:
 
(...)
 
5. Dose escalation will be stopped if at least 2 subjects on active treatment at one dose level have relevant individual QT prolongations, i.e. a QTc increase of greater than 60 ms from
   |

Proprietary confidential information © 2021 Boehringer Ingelheim International GmbH or one or more of its affiliated companies

|                              |   |
|------------------------------|---|
|                              | 
baseline in connection with absolute QT or QTc greater than 500 ms, as confirmed by a repeat ECG recording
 
(...)
 
To:
 
(...)
 
5. Dose escalation will be stopped if at least 2 subjects on active treatment at one dose level have relevant individual QT prolongations, i.e. a QTc increase of greater than 60 ms from baseline, or absolute QT or QTc greater than 500 ms, as confirmed by a repeat ECG recording
 
(...)
  |
| Rationale for change  | To clarify the QT related discontinuation criteria  |
|                              |   |

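### Exclusion criterion 22 requires a positive SARS-CoV-2 test plus symptoms, while Section 1.4.3 excludes on the test alone and cites a criterion 25 that does not exist (minor correction)

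*Protocol*

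**What the plan says.** - **Section 3.3.3, criterion 22**, the last on the list, excludes on "A positive for SARS-CoV-2 specific test and clinical symptoms suggestive for this disease at screening visit" or in the 3 days before admission.
- **Section 1.4.3, Safety measures**, states: "Subjects positive in the SARS-CoV-2 test are not eligible to the trial in accordance to exclusion criterion 25". It adds that these subjects will be kept out of the trial.
- **Section 5.2.4, Table 5.2.4: 2** places the SARS-CoV-2 test among the exclusionary laboratory tests and attaches no symptom condition.
- **Section 3.3.4.1, item 7** ends participation if "The patient experiences an infection with SARS-CoV-2", again whether or not there are symptoms.
- **Section 8.3.1** requires documented evidence before allocation "that the trial participant meets all inclusion criteria and does not meet any exclusion criteria".

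**The concern.** The numbered list in Section 3.3.3 is what a site checks and documents before allocation, and criterion 22 is the only numbered criterion that names this test. Taken literally, it leaves a test-positive volunteer without symptoms unexcluded. A reader who turns from Section 1.4.3 to the list for the stricter rule finds no item 25.

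What is at stake is the safety of people housed together. Subjects stay at the site for at least 48 hours after dosing, and Flow Chart footnote 14 allows a stay until Day 5. Section 1.4.3 requires a subject who tests positive during the trial to stop treatment at once and be isolated from the others. The entry rule should not be looser than that.

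**Working it through.** No formula applies and the plan gives no figure to reproduce. The check compares the current texts case by case and then traces the wrong number.

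**Step 1. Apply each rule to the four possible subjects.**

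| Test | Symptoms | Criterion 22, read literally | Section 1.4.3 |
|---|---|---|---|
| Positive | Yes | Excluded | Not eligible |
| Positive | No | Not excluded | Not eligible |
| Negative | Yes | Not excluded | Silent |
| Negative | No | Not excluded | Silent |

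The rules part only in the second row.

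**Step 2. Decide which text is the outlier.** Section 1.4.3 and Table 5.2.4: 2 both make the test sufficient. The schedule fits them. Flow Chart footnote 13 tests every subject at screening and again in the 3 days before admission, with or without symptoms; the second test may be dropped only when screening falls on Days -3 to -1. Routine testing of this kind has little purpose if a positive result without symptoms does not exclude. Item 7 of Section 3.3.4.1 points the same way, although it is a discontinuation rule and so weaker evidence on eligibility. Criterion 22 stands alone.

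**Step 3. Check the cross-reference.** The list in Section 3.3.3 runs unbroken from 1 to 22, and the next line moves on to study restrictions. There is no item 25.

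**Step 4. Trace the number.** Global Amendment 1 (Section 11.1) restructured the list, for the stated reason "To clarify the exclusion criteria for concomitant disease and medical history". Six numbered items (4 to 9) became three (4 to 6):

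- numbers removed: 6 - 3 = 3
- former item 25 becomes 25 - 3 = 22

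This fits a reference in Section 1.4.3 that was not updated and that was always meant for the present criterion 22. The log serves only to explain where 25 came from. The error lies between two current texts.

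**Step 5. See what else could stop the subject.**

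- Section 1.4.3 itself states the intended rule.
- Criterion 4, "Any evidence of a concomitant disease assessed as clinically relevant by the investigator", includes relevant acute infections, but depends on judgement.
- Criterion 19 covers a subject who "has a condition that would not allow safe participation in the study", also by judgement.
- Item 7 of Section 3.3.4.1 could act before dosing. Section 3.3.4 foresees that case in general terms, in a provision that begins "If a subject discontinues trial participation prior to the administration of trial medication". It does not mention SARS-CoV-2, so this is an inference.

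**The case against.** The best reply is that the two texts can both be obeyed. Exclusion criteria list what bars entry; failing to meet criterion 22 does not make anyone eligible. A site that turns away every test-positive volunteer satisfies criterion 22 and Section 1.4.3 together. On this view criterion 22 is too narrow and is not a contrary command. That is fair, and it is one reason the point is rated low. It does not make criterion 22 right: a site working from the numbered list alone would pass the subject on that item.

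The conjunction might also be read loosely, as two separate grounds. That is not its plain sense, and a wording open to both readings would still need correcting.

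The amendment explanation is an inference. Section 11.1 does not show the old item 25 or its text, so the arithmetic is consistent with renumbering but does not prove it. The dead reference stands either way.

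Finally, editing an eligibility criterion is not free. Under Section 8.1, changes made by amendment need the same ethics and authority approval as the protocol. The SAP, final on 16 December 2021, speaks of the study in the past tense (Sections 6.5 and 8), so by that date an amendment may have had little practical use. These points limit the weight and timing of the correction. They do not remove the inconsistency.

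**Conclusion.** The concern holds, as a minor correction. Criterion 22 is wrong as written against the rule the sponsor states in Section 1.4.3, and that section's reference to criterion 25 leads nowhere. The reference is off by 3.

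Only test-positive subjects without symptoms are affected. How many would present is not stated, and none of the 32 may be concerned. The sample size is not based on a power calculation (Section 7.7), and no endpoint, analysis set or planned analysis depends on this criterion.

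The conclusion rests on the plain meaning of the conjunction in criterion 22 and on taking Section 1.4.3, supported by Table 5.2.4: 2, as the intended rule. It does not rest on the renumbering explanation.

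**What to change.** Let the Section 1.4.3 rule govern.

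1. Reword criterion 22 along these lines: *Positive SARS-CoV-2 specific test, regardless of symptoms, at screening or in the 3 days before admission.*
2. In Section 1.4.3, change the cited criterion from 25 to 22.

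Simply replacing the conjunction with *or* would go further: it would also exclude volunteers with symptoms and a negative test, on whom Section 1.4.3 is silent. If the sponsor wants that too, it should say so expressly.

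The cost is one line and one number in a minor protocol amendment, plus the approval step in Section 8.1. It could be carried with any other amendment. It adds no procedure and leaves sample size and analysis unchanged.

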### 3.3.4 Withdrawal of subjects from treatment or assessments

Subjects may discontinue trial participation by withdrawing consent to trial participation as a whole ('withdrawal of consent') or by being removed from the trial by the investigator; please see Section 3.3.4.1 below.

If a subject discontinues trial participation prior to the administration of trial medication, the data of this subject will not be entered in the case report form (CRF) and will not be reported in the clinical trial report (CTR). If a subject discontinues trial participation after administration of trial medication, this will be documented and the reason for discontinuation of trial participation must be recorded in the CRF; in addition, the data will be included in the CRF and will be reported in the CTR.

At the time of discontinuation of trial participation, a complete end of trial examination will be performed, if possible, and the information will be recorded in the CRF. If the discontinuation occurs before the end of the REP (see Section [1.2.7](#)), the discontinued subject should if possible be questioned for AEs and concomitant therapies at or after the end of the REP in order to ensure collection of AEs and concomitant therapies throughout the REP, if not contrary to any consent withdrawal of the subject.

Since the risks of drug exposure of a pregnant partner of a study participant via the seminal fluid are yet unknown, adequate contraception as outlined in Section [3.3.2](#), is a prerequisite for participation in the study and is still necessary even if the subject withdraws consent or is removed from the trial.

#### 3.3.4.1 Discontinuation of trial participation

An individual subject will discontinue trial participation if:

1. The subject wants to discontinue trial participation (withdrawal of consent), without the need to justify the decision
2. The subject has repeatedly shown to be non-compliant with important trial procedures and, in the opinion of both, the investigator and sponsor representative, is not willing or able to adhere to the trial requirements in the future
3. The subject needs to take concomitant medication that interferes with the investigational medicinal product or other trial treatment

Proprietary confidential information © 2021 Boehringer Ingelheim International GmbH or one or more of its affiliated companies

4. The subject can no longer participate in this trial for medical reasons (such as surgery, adverse events [AEs], or diseases)
5. An AE or clinically significant laboratory change or abnormality occurs that the investigator assesses as warranting discontinuation of trial participation. This may include cases of sustained symptomatic hypotension (BP <90/50 mmHg) or hypertension (BP >180/100 mmHg), clinically relevant changes in ECG requiring intervention, or unexplained hepatic enzyme elevations at any time during the trial
6. The subject has an elevation of AST and/or ALT  $\geq$ 3-fold upper limit of normal (ULN) and an elevation of total bilirubin  $\geq$ 2-fold ULN (measured in the same blood sample) and/or needs to be followed up according to the DILI checklist provided in the ISF
7. The patient experiences an infection with SARS-CoV-2 (see Section [5.2.4](#))

In addition to these criteria, the investigator may discontinue subjects at any time based on his or her clinical judgment.

Even if the trial participation is discontinued, the subject, given his agreement, will undergo the procedures for early trial treatment discontinuation and follow up as outlined in the [Flow Chart](#) and section [6.2.3](#).

In case of discontinuation of trial participation according to item #1 above, the investigator should be involved in the discussion with the subject and explain the options for continued follow up.

